4.2. Benefits

As this is a retrospective study, there are no physical benefit to individual research subjects; however, society and physicians will benefit from the knowledge gained.

5. Data Analysis

Since this is a retrospective study, analyses will consist of tabulated data and descriptive statistics. Subject data listings and tabular and graphical presentations of the summary and statistical results will be provided. Additional quantitative and qualitative comparisons will be made between the groups of subjects, contemporary literature, and similar studies.

Statistical comparisons between treatment groups (CanGaroo versus Tyrx versus no envelope) will be performed using Fisher's exact test or Chi-square tests for categorical variables. Continuous variables will be analyzed using ANOVA. A log rank test will be performed to compare the time to infection between the CanGaroo, Tyrx, and no envelope treatment groups at all of the follow-up visits.

	TYPE: Protocol	Document	CPR-2212
	TITLE: RETROSPECTIVE EXPERIENCE OF CIED IMPLANTATION WITH PIEDMONT ATHENS REGIONAL ELECTROPHYSIOLOGY	Revision	C
		Page 8 of 9	

6. Ethical Considerations

6.1. *Code of Conduct*

The Investigator will ensure that the clinical study is conducted in accordance with good clinical practice and all regulatory and institutional requirements, including those for subject privacy, informed consent, Institutional Review Board, or Ethics Committee approval, and record retention.

6.2. *Institutional Review Board Approval and Oversight*

This protocol, or any subsequent modifications, will be reviewed and approved by an Institutional Review Board. A Waiver of Informed Consent and HIPAA due to the retrospective nature of this study will be requested.

The confidentiality of the identity of subjects enrolled in the study and the information contained in their study records will be maintained. Any publication of any data collected as part of this trial will only use de-identified data, so that identification of any individual subject will not be possible.

The records will be made available as required for review by the FDA, or other applicable regulatory agency and a reviewing IRB; however to the extent possible, the subject's identity will not be disclosed.

A subject identification number will be used during data collection and the patient name, date of birth, medical record number and/or address will NOT appear anywhere.

	TYPE: Protocol	Document	CPR-2212

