	TITLE: RETROSPECTIVE EXPERIENCE OF CIED IMPLANTATION WITH PIEDMONT ATHENS REGIONAL ELECTROPHYSIOLOGY	Revision	C
		Page 4 of 9	

Study Synopsis

COMPANY	Aziyo Biologics, Inc.
PROTOCOL No.	CPR-2212
PRODUCT(S)	CanGaroo® Envelope and Tyrx™ Absorbable Antibacterial Envelope
PROTOCOL TITLE:	Retrospective Experience of CIED Implantation with Piedmont Athens Regional Electrophysiology
OBJECTIVE	The objective of this study is to retrospectively gather information on patients who underwent a CIED procedure with either a CanGaroo, Tyrx envelope, or no envelope.
DESIGN	A single center will retrospectively review up to 700 subjects who underwent implantation of a CIED with CanGaroo, Tyrx, or no envelope. All sets of subjects enrolled will also be examined for any follow-up visits and/or adverse events that occurred up to 12 months post-surgery.
STUDY POPULATION	Male or female patients who underwent a CIED implantation utilizing CanGaroo hydrated in saline, CanGaroo hydrated in Antibiotic, Tyrx, or no envelope.
ENDPOINTS	The endpoints will be defined as: 
 1. The incidence of major infection post procedure. 2. Any pocket related issues that prompted an office visit
CLINICAL PARAMETERS	The following clinical data will be collected 
 • Demographic information • Risk factors for infection • Surgical procedure • Type of device implanted • Envelope soak solution used • Post procedure information on major infections as defined below • Post procedure information on pocket related issues • Post procedure information on hematoma
DURATION	Data will be collected for a minimum of one post-surgical visit after CIED implant for all groups. If more visits are available, data from those visits will be collected up to 12 months post-procedure.
CENTERS	Single center in the U.S.

	TYPE: Protocol	Document	CPR-2212
	TITLE: RETROSPECTIVE EXPERIENCE OF CIED IMPLANTATION WITH PIEDMONT ATHENS REGIONAL ELECTROPHYSIOLOGY	Revision	C
		Page 5 of 9	

1. Introduction and Rationale

This document is a protocol for a human research study. This study is to be conducted according to U.S. and international standards of Good Clinical Practice in accordance with applicable Federal regulations, International Conference on Harmonization guidelines, and institutional research policies and procedures.

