Broader indications for the implant of cardiac implantable electronic devices (CIED) and population aging are the main reasons for the continuous increase in the use of pacemakers, implantable cardioverter-defibrillators, and devices for cardiac resynchronization therapy. The rate of infection is out of proportion to the increase in implantation rate. This is primarily due to the comorbidities in CIED patients, the greater complexity of the devices, and the increased duration of procedures.^{1,2,3}

2. Study Design and Methods

Clinical records will be reviewed and data collected for up to 700 subjects who underwent implantation of a CIED. All sets of subjects will have data reviewed for any visits on or after March 27, 2017. No subject will be excluded from the study based on gender, racial, or ethnic origin. Patients will not be contacted and only de-identified data will be collected. A waiver of Informed Consent and HIPAA authorization will be requested from the IRB.

Each patient's medical records will be reviewed by the investigator or designated personnel for basic clinical data, including demographic information, risk factors for infection, information about the surgical procedure, type of device implanted, and post procedure information on infection, pocket related issues, and hematoma information will all be collected for each subject. Data will be collected retrospectively using Electronic Data Capture (Medrio).

CIED infections are defined as (1) superficial cellulitis in the region of the CIED pocket with wound dehiscence, erosion, or purulent drainage, (2) deep incisional or organ/space (generator pocket) surgical site infection that meets the Centers for Disease Control and Prevention criteria, independent from time of surgery, (3) persistent bacteremia, or (4) endocarditis.

Major CIED infections are defined as a CIED infection resulting in one or more of the following:

- CIED system removal
- Any invasive procedure (e.g., pocket opened) without system removal

	TYPE: Protocol	Document	CPR-2212
	TITLE: RETROSPECTIVE EXPERIENCE OF CIED IMPLANTATION WITH PIEDMONT ATHENS REGIONAL ELECTROPHYSIOLOGY	Revision	C
		Page 6 of 9	

- Treatment with antibiotic therapy if the subject is not a candidate for system removal and infection recurrence after completion of antibiotic therapy or evidence of deep infection with wound dehiscence, erosion, or purulent drainage
- Death

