2.1 Schedule of Assessments

	Pre-Procedure Screening Visit	Procedure Visit	Follow-up Visits (up to 12 mo.)	Unscheduled Visit
Inclusion Determination	X			
Baseline Demographics	X			
Medical History/Risk Factors	X			
Type of Device Implanted		X		
Envelope Soak Solution Used		X		
Procedure Details		X		
Documentation of Complications		X		
Post-Operative Events			X	X
Infection Information/Culture Results			X	X
Pocket Related Issues			X	X

	TYPE: Protocol	Document	CPR-2212
	TITLE: RETROSPECTIVE EXPERIENCE OF CIED IMPLANTATION WITH PIEDMONT ATHENS REGIONAL ELECTROPHYSIOLOGY	Revision	C
		Page 7 of 9	

3. Study Objectives

The objective of the study is to:

1. The objective of this study is to retrospectively gather information on patients who underwent a CIED procedure with either a CanGaroo, Tyrx envelope, or no envelope.

Endpoints

The endpoints are defined as:

1. The incidence of major post procedure infection (as defined above)
2. Any pocket related issues that prompted an office visit which include but are not limited to pain, swelling, redness, migration and/or hematoma

4. Risks and Benefits

4.1.Risks

As this is a retrospective study, there are no physical potential risks to research subjects. There may be risks associated with loss of privacy.

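### Section 5 compares both endpoints between non-randomised envelope groups only by unadjusted tests; the collected risk factors have no role in those endpoint comparisons

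*Combined protocol and SAP*

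**What the plan says.** The Synopsis and Section 2 describe a single-center retrospective review of up to 700 patients with CanGaroo, Tyrx or no envelope. No randomisation, matching or group sizes are stated, and the text available for this review does not say how the envelope was chosen.

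Section 5 opens descriptively: "Since this is a retrospective study, analyses will consist of tabulated data and descriptive statistics". It then commits to formal tests: "Statistical comparisons between treatment groups (CanGaroo versus Tyrx versus no envelope) will be performed using" Fisher's exact or chi-square tests for categorical variables, with ANOVA for continuous ones. It adds: "A log rank test will be performed to compare the time to infection between the CanGaroo, Tyrx, and no envelope treatment groups".

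Section 3 has two endpoints. One is the incidence of major infection. The other is: "Any pocket related issues that prompted an office visit which include but are not limited to pain, swelling, redness, migration and/or hematoma". Both are categorical as stated, so both fall under the Fisher/chi-square plan.

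The data needed for adjustment are collected. The Synopsis lists "Risk factors for infection • Surgical procedure • Type of device implanted" along with demographics, and the Schedule of Assessments (Section 2.1) has a row for "Medical History/Risk Factors".

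On follow-up, the Synopsis says: "Data will be collected for a minimum of one post-surgical visit after CIED implant for all groups". Later visits are used where available, up to 12 months.

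**The concern.** Without randomisation, envelope groups may differ in infection risk before any envelope is placed. The crude test then mixes case mix with any envelope effect. It could suggest a difference that is not there or hide one that is, and reviewing more charts does not remove the problem.

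The introduction treats patient and procedure factors as prognostic. Of the rise in infection it says: "This is primarily due to the comorbidities in CIED patients, the greater complexity of the devices, and the increased duration of procedures". Variables of that kind are collected, yet none enters the endpoint comparisons as a covariate, stratum or weight. At stake is whether a reported difference, or lack of one, between CanGaroo, Tyrx and no envelope can be interpreted at all.

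**Working it through.** The plan has no figure to reproduce: it gives no expected rate, effect size, alpha, power or group sizes. What follows illustrates a mechanism; every rate, share, group size and follow-up pattern is an assumption.

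**1. Bias in the infection comparison.** Assume one binary risk factor, no envelope effect, and infection risks of 3% (high risk) and 0.5% (other). Crude risk = share × 3% + (1 − share) × 0.5%.

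| High-risk share, CanGaroo/Tyrx/none | Envelope groups | No envelope | Difference |
|---|---|---|---|
| Strong, 60/60/20% | 0.6×3 + 0.4×0.5 = 2.0% | 0.2×3 + 0.8×0.5 = 1.0% | 1.0 point |
| Moderate, 60/60/40% | 2.0% | 0.4×3 + 0.6×0.5 = 1.5% | 0.5 point |
| Mild, 50/50/40% | 0.5×3 + 0.5×0.5 = 1.75% | 1.5% | 0.25 point |

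**2. Masking.** If both envelopes truly halved the risk, the strong case gives 0.6×1.5% + 0.4×0.25% = 1.0% in the envelope groups against 1.0% without. A real benefit would look like none.

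**3. Pocket issues.** With risks of 12% and 5%, the strong case gives 0.6×12 + 0.4×5 = 9.2% against 0.2×12 + 0.8×5 = 6.4%. The mild case gives 8.5% against 7.8%.

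**4. False-positive rate.** Simulated three-group chi-square test at 0.05, strong imbalance, no envelope effect, 200,000 runs:

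| Group sizes, CanGaroo/Tyrx/none | Infection | Pocket, 12% vs 5% | Pocket, 15% vs 4% |
|---|---|---|---|
| 234/233/233 | 0.11 | 0.18 | 0.39 |
| 450/200/50 | 0.03 | 0.05 | 0.08 |
| 100/100/500 | 0.22 | 0.23 | 0.45 |

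With equal groups and mild imbalance the rates are 0.05, 0.06 and 0.07. For the log-rank test on infection, equal groups and strong imbalance, the rate is 0.11 if everyone has 12 months but about 0.06 if follow-up varies. The rejection rate therefore depends heavily on group sizes and follow-up that the plan does not give. The bias in steps 1 to 3 does not depend on group sizes.

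**5. Whether adjustment works with few events.** With equal groups, about 12 infections are expected in the strong case (467 × 2.0% + 233 × 1.0% = 11.7). In simulations of that case with full follow-up and a true hazard ratio of 1, the median CanGaroo-versus-none hazard ratio was 1.81 unadjusted. It was 0.95 from a Firth-penalised Cox model containing the risk factor. Coverage of the 95% profile interval was 0.894 unadjusted and 0.965 adjusted. With follow-up of 0.5 to 12 months the medians were 1.71 and 0.91. Weighted Wald intervals for infection excluded zero in 0.092 of null runs, so they are unsuitable here.

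**6. Why follow-up must enter the pocket analysis too.** Take balanced case mix (half high-risk, 12-month risks 12% and 5%, constant hazard) and no envelope effect. If follow-up is uniform over 0.5–12 months in one group and 0.5–6 months in another, the observed proportions are 4.5% and 2.4%. Weighting on baseline variables would not correct that.

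**The case against.** The best defence is the stated purpose. The only objective is to gather information, Section 5 opens as descriptive, and there is no hypothesis, alpha or causal claim. That lowers the severity. It does not dispose of the point, because the same section goes on to commit to significance tests between groups it calls treatment groups.

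Section 5 also mentions additional comparisons between groups and with the literature. No method, variable or endpoint is attached to them, so they do not prespecify adjustment.

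Three stronger readings are tempting, and the documents do not support them:

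- *The plan ignores risk factors.* Section 5 applies its tests to categorical and continuous variables generally. Neither endpoint is continuous as stated, so ANOVA most naturally applies to baseline or procedural data. Risk factors may well be compared between groups. That would show imbalance but not correct the endpoint comparison.
- *The introduction shows that the groups differ.* It names drivers of infection in CIED patients at large and says nothing about who received which envelope.
- *The tests have a known, inflated error rate.* Step 4 of the working shows rates from below 5% to well above it under the same imbalance.

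It is also fair to say that adjustment gains little power for infection. With a true hazard ratio of 0.5, strong imbalance and full follow-up, the adjusted overall test rejected in only 0.086 of runs. The case for adjusting rests on reducing bias, not on power.

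**Conclusion.** The point holds. Both endpoints are to be compared between non-randomised groups by unadjusted tests only, and the risk factors already being collected play no part in those comparisons.

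The firm harm is a biased estimate of unknown direction and size. Under the strong assumed imbalance it doubles the apparent infection risk (2.0% against 1.0%) with no envelope effect; under the mild one it is 0.25 points. False-positive rates are illustrative only. Actual imbalance is not shown by the documents, but without a described allocation rule balance cannot be assumed either. The point should be fixed before analysis; given the descriptive framing it is not fatal to the study.

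**What to change.** In Section 5, prespecify one adjusted between-group comparison per endpoint. Use variables fixed before the envelope was placed and already collected (demographics, infection risk factors, procedure type, device type), and a method that allows for unequal follow-up.

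- **Major infection:** a Firth-penalised Cox model with envelope group and one or two risk factors named in advance, with profile-likelihood 95% intervals. This is the adjusted counterpart of the planned log-rank test.
- **Pocket-related issues:** a time-to-first-event analysis. Examples are a Cox model with a short prespecified covariate list, or a propensity-weighted Cox or Kaplan-Meier comparison with robust intervals. A plain risk difference that ignores follow-up is not adequate. If overlap weights are used, state that the result applies to patients who could plausibly have received any of the three options.
- **Balance:** tabulate risk factors and length of follow-up by group, with standardised differences.
- **Planned tests:** keep the Fisher/chi-square and log-rank results, labelled unadjusted and descriptive, with no causal reading.

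The cost is SAP wording and two modest analyses on data already collected. Intervals will be somewhat wider, power for infection stays low with or without adjustment, and unmeasured confounding remains.

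### Should Section 5 have committed to separate results for saline-soaked and antibiotic-soaked CanGaroo?

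*Combined protocol and SAP*

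**What the plan says.** The Study Synopsis, STUDY POPULATION row, describes eligible patients as those implanted with "CanGaroo hydrated in saline, CanGaroo hydrated in Antibiotic, Tyrx, or no envelope". The CLINICAL PARAMETERS row lists "Envelope soak solution used", and the Schedule of Assessments (Section 2.1) places "Envelope Soak Solution Used" at the procedure visit.

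The DESIGN row speaks of "up to 700 subjects who underwent implantation of a CIED with CanGaroo, Tyrx, or no envelope". The OBJECTIVE row and Section 3 use the same three categories.

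Section 5 opens by saying that "analyses will consist of tabulated data and descriptive statistics", and promises subject data listings. It adds: "Additional quantitative and qualitative comparisons will be made between the groups of subjects, contemporary literature, and similar studies". It then names its tests. For categorical variables: "Statistical comparisons between treatment groups (CanGaroo versus Tyrx versus no envelope) will be performed using" Fisher's exact or chi-square tests. For the log-rank test, the aim is to "compare the time to infection between the CanGaroo, Tyrx, and no envelope treatment groups". The ANOVA sentence names no groups. Soak is not mentioned in Section 5.

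**The concern.** The population row has four exposure categories and the named tests have three. One soak contains an antibiotic and the other does not, and the first endpoint is major infection, so a reader may expect soak to matter. It is singled out in the population description and abstracted from each chart, and then has no stated use in the analysis.

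If infection or pocket-related risk did differ by soak, the CanGaroo rate would be a weighted average that depends on this one centre's habits, and might not carry over to a site that uses a single soak. In a retrospective study the outcomes have already occurred, so an optional split could also be shown or withheld after the results are known.

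**Working it through.** **1. Do the passages conflict?** Set side by side:

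| Place | What it does | CanGaroo split by soak? |
|---|---|---|
| Synopsis, STUDY POPULATION | says whose charts are eligible | yes |
| Synopsis, CLINICAL PARAMETERS; Section 2.1 | says what is collected | soak recorded |
| Synopsis, OBJECTIVE and DESIGN | says what the study is about | no |
| Section 3 | objective | no |
| Section 5, categorical tests and log-rank | says what is compared | no |

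The only place that separates the soaks is an eligibility description. Every place that states the study question names CanGaroo once, and the named tests follow the study question. Recording a variable does not oblige the plan to stratify by it: demographics, infection risk factors and device type are also collected, and Section 5 names no breakdown by any of them.

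**2. Is a result by soak ruled out?** No. The data are collected, and tabulations, listings and further comparisons between groups are promised. A table by soak, with the mix stated, fits that wording without an amendment.

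**3. How much could turn on it?** The plan has no figure to reproduce. Its 700 is a ceiling, with no group sizes, rates or soak mix. Everything below is assumed.

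Pooled rate = m × saline rate + (1 − m) × antibiotic rate, where m is the saline share:

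| Assumed saline / antibiotic rates | m = 0.2 | m = 0.5 | m = 0.8 |
|---|---|---|---|
| infection 1.5% / 1.5% | 1.5% | 1.5% | 1.5% |
| infection 2.0% / 1.0% | 1.2% | 1.5% | 1.8% |
| pocket issues 10% / 5% | 6.0% | 7.5% | 9.0% |

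For example, 0.8 × 2.0% + 0.2 × 1.0% = 1.8%. The shift simply restates the assumed two-fold ratio. It is not evidence that such a ratio exists here.

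**4. What would the extra table show?** Assume 700/3 ≈ 233 CanGaroo charts, split 116 saline and 117 antibiotic, with exact (Clopper-Pearson) 95% intervals for the rates and Newcombe intervals for the differences:

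- Infection: 2/116 = 1.7% (0.2% to 6.1%) against 1/117 = 0.9% (0.0% to 4.7%). Difference +0.9 points (−3.2 to +5.3).
- Pocket issues: 12/116 = 10.3% (5.5% to 17.4%) against 6/117 = 5.1% (1.9% to 10.8%). Difference +5.2 points (−1.9 to +12.6).

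By full binomial enumeration, the chance that the interval for the difference excludes zero is:

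| Assumed true rates | 116 / 117 | 47 / 186 |
|---|---|---|
| infection 2.0% v 1.0% | 3.0% | 7.9% |
| pocket issues 10% v 5% | 28.1% | 28.1% |

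With the 20/80 split (47 saline, 186 antibiotic) and true infection rates of 2.0% and 1.0%, the chance of no saline infections at all is 0.98^47 = 0.39, and 0/47 has an upper exact limit of 7.5%. The observed saline rate would be no higher than the antibiotic rate about 43% of the time, although the true risk is doubled.

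**The case for a change.** The best case for raising the point is that permission is not commitment. The text on further comparisons does not mention soak and does not define its groups, so whether a split appears can be decided after the results are seen. One sentence using data already collected would remove that discretion, and a purely descriptive table adds no tests and no multiplicity.

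Part of this stands. Section 5 does not commit to a table by soak, the sponsor itself singled out soak in the population row, and such a table would be cheap. But this is an argument for an optional addition. It shows no fault in the planned comparisons, which answer the stated objective whatever the soak mix. The table would alter none of those comparisons, and for infection it would seldom distinguish the soaks. It is also less tidy than it sounds: with chart abstraction some records may lack a soak or name another one, so two columns need not add up to the CanGaroo total.

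**Conclusion.** The concern does not hold. Section 5 compares the three envelope groups that the objective, the design and Section 3 define. The four-way wording in the population row describes who is eligible and creates no fourth analysis group. Soak is recorded, and the promised tabulations and additional comparisons allow it to be reported. Leaving that table optional is a missing detail that the analysts can fill, and it invalidates no planned result.

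The reading of the text needs no numerical assumption. The size does: the range of 1.2% to 1.8% for the pooled infection rate, and the 3% chance of telling the soaks apart, rest on assumed rates, an assumed third of 700 charts in CanGaroo and an assumed soak mix. If the risks are equal, pooling has no effect on the rate. One limit remains: some pages are not in the public text, so it cannot be checked whether they define the groups further. Section 5 itself is available, and the conclusion rests on it and on the objective and design statements.

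### Section 5 requires a three-group log rank test with no small-sample version and gives no rule for choosing between Fisher and chi-square; with few infections and one small group, small p-values could be several-fold too small

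*Combined protocol and SAP*

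**What the plan says.** The Synopsis lists as its first endpoint "The incidence of major infection post procedure". Its Design row sets the scale: "A single center will retrospectively review up to 700 subjects". No section says how many subjects each envelope group will hold, and in a chart review the design does not fix those numbers.

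Section 5 sets out the comparison ("CanGaroo versus Tyrx versus no envelope"). For proportions it offers Fisher's "exact test or Chi-square tests for categorical variables", with no criterion for choosing between them. For timing it states: "A log rank test will be performed to compare the time to infection between the CanGaroo, Tyrx, and no envelope treatment groups". It does not say how the log rank p-value is obtained, and it sets no minimum number of events. The documents contain no expected infection rate, significance level or power statement.

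On follow-up, the Synopsis says: "Data will be collected for a minimum of one post-surgical visit after CIED implant for all groups". Later visits are used where they exist, up to 12 months, so follow-up length will vary between subjects and perhaps between groups.

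**The concern.** The usual p-values of the chi-square and log rank tests both rest on a large-sample chi-square distribution, here with 2 degrees of freedom. That approximation is poor when a group is expected to contribute less than about one event. Major infection may be rare, and 700 is a ceiling shared among three groups whose sizes follow past practice.

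One or two infections in a small envelope group could then give a striking p-value on weak evidence, and a reader could take it as a difference between named products. Naming Fisher's test protects only the comparison of proportions. The log rank test is mandatory and has no corresponding protection. Without a selection rule, the choice between Fisher and chi-square could also be made after both results are seen.

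**Working it through.** The plan states no event count, power or significance level, so it has no figure of its own to reproduce.

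**Inputs**
- From the documents: at most 700 subjects (Synopsis, Section 2); three groups (Section 5); follow-up from one visit up to 12 months (Synopsis).
- Assumed, because the documents are silent: infection rates of 0.5%, 1% and 2%; splits of the 700 from 234/233/233 to 600/50/50; nominal levels of 5% and 1% as yardsticks.

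**Step 1: expected events.** In total, 700 × 0.005 = 3.5, 700 × 0.01 = 7 and 700 × 0.02 = 14. In the smallest group the expected count is rate × n:
- n = 50: 0.25, 0.5 and 1.0
- n = 150: 0.75, 1.5 and 3.0
- n = 233: 1.2, 2.3 and 4.7

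An expected count of 5 in the smallest group needs a rate of 5/233 = 2.1%, 5/150 = 3.3% or 5/50 = 10%.

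**Step 2: the extreme case, one event.** If the only event falls in a group of n out of N at risk, the log rank statistic is N/n − 1 = 700/50 − 1 = 13. On 2 degrees of freedom, p = exp(−13/2) = 0.0015. With no group difference, the chance that a single event lands in that group is 50/700 = 0.07. If a second group also has 50 subjects, a result this extreme has probability 100/700 = 0.14.

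**Step 3: individual tables.** Given the total number of events, their distribution over the groups under no difference is multivariate hypergeometric and can be enumerated. The log rank column uses the rare-event form, the sum of (O − E)²/E, with equal follow-up.

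| Group sizes | Events | Chi-square p | Log rank p | Exact p of the chi-square statistic | Fisher-Freeman-Halton p |
|---|---|---|---|---|---|
| 500/150/50 | 1/0/2 | 0.0003 | 0.0003 | 0.014 | 0.034 |
| 500/150/50 | 2/0/2 | 0.0032 | 0.0034 | 0.029 | 0.032 |
| 600/50/50 | 3/0/2 | 0.015 | 0.016 | 0.086 | 0.086 |
| 350/200/150 | 1/0/3 | 0.030 | 0.030 | 0.039 | 0.039 |

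The gap is large when the smallest group has 50 subjects and slight in the milder split.

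**Step 4: average size of chi-square.** Conditional sizes were averaged over a binomial event count.
- Nominal 5%, rate 1%: 0.042 (equal groups), 0.044 (350/200/150), 0.055 (500/150/50), 0.057 (550/100/50) and 0.063 (600/50/50).
- Nominal 5%, rate 2%, last three splits: 0.047, 0.047 and 0.053.
- Nominal 1%, rate 1%: 0.005 (equal), 0.007 (350/200/150), 0.018 (500/150/50) and 0.027 (600/50/50).

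**Step 5: size of the log rank test.** This was simulated with 6000 runs per setting, a 12-month cap and random shorter follow-up. The simulation error is about √(0.05 × 0.95/6000) = 0.003 at 5% and √(0.01 × 0.99/6000) = 0.0013 at 1%. Each cell shows the size at nominal 5% / nominal 1%.

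| Group sizes | Rate 0.5% | Rate 1% | Rate 2% |
|---|---|---|---|
| 234/233/233 | 0.020 / 0.001 | 0.037 / 0.004 | 0.042 / 0.007 |
| 500/150/50 | 0.064 / 0.027 | 0.060 / 0.024 | 0.050 / 0.019 |
| 600/50/50 | 0.079 / 0.052 | 0.073 / 0.038 | 0.062 / 0.027 |

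**Step 6: the replacements.** The Fisher-Freeman-Halton test stayed below 0.05 in every setting tried (about 0.014 to 0.049). A Monte Carlo log rank reference that draws the group at each event time in proportion to the subjects at risk held nominal size to within simulation error. It was usually below nominal, and this was so with unequal censoring as well.

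**The case against.** The strongest reply is that the harm needs two facts the documents do not supply: few events and a group near 50. With equal groups or a 350/200/150 split, both tests are at or below nominal. This stands, and it limits the point to a conditional one. The log rank event is infection, not major infection, and Section 2 defines infection more broadly, so events may be more numerous than the first endpoint suggests. This also stands.

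Fisher's test is named first, and many analysts would read the wording as Fisher where cells are sparse. That is fair. For proportions the gap is only an unstated selection rule, and nothing in the plan says chi-square will be used for infection.

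Section 5 opens by describing the analysis as descriptive, and the plan has no decision rule. A p-value of 0.0015 from one infection would probably sit beside counts of 0, 0 and 1. This lowers the stakes, but Section 5 still commits to formal tests between named products.

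A reader might infer more than this in three ways, and none is supported:
- **That false positives at 5% will be roughly doubled.** With exactly six events, chi-square size is 0.083 (500/150/50), 0.103 (550/100/50) and 0.123 (600/50/50). Six is the worst total for these splits. With seven events the figures are 0.050, 0.032 and 0.023, and the averages in Step 4 are close to nominal.
- **That the smallest group must expect fewer than one event.** Step 1 shows that this fails over much of the assumed range.
- **That a Fisher p well above the chi-square p measures only the failure of the approximation.** For 550/100/50 with events 4/0/2, chi-square gives 0.034 and Fisher-Freeman-Halton 0.103, but the exact p of the chi-square statistic itself is 0.054. Much of the gap comes from how the two tests order the tables.

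**Conclusion.** The point holds as a conditional weakness that is cheap to remove. The plan requires a log rank test with no small-sample version and leaves the choice between Fisher and chi-square open. If the infection rate is 0.5% to 2% and the smallest group is about 50, asymptotic p-values below about 0.01 can be several-fold too small. The log rank size is then about two to five times nominal at 1% (0.02 to 0.05), against 0.05 to 0.08 at a nominal 5%. Single tables can be further out, as the one-event case shows.

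Both the rate and the splits are assumptions. Where groups are equal or mildly unequal the problem does not arise, and at higher infection rates it shrinks. The documents do not support a claim that the planned tests are invalid in general or that a false envelope difference is likely. This is a desirable improvement, not a flaw that undermines the study.

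**What to change.** In Section 5, before the data are analysed:

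1. State that infection proportions are compared with the Fisher-Freeman-Halton exact test, and that chi-square is used for categorical variables only where all expected counts are at least 5.
2. State that the log rank p-value comes from a Monte Carlo risk-set conditional permutation distribution: at each event time the group is drawn in proportion to the subjects then at risk. This allows for groups with different follow-up.
3. Report the number of infections and subjects per group beside every such p-value.

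The cost is one or two sentences and a few lines of code, with no new data. The downside is mild conservatism when events are very few. If the sponsor prefers to stay purely descriptive, infection counts with exact confidence intervals and no test would also remove the problem.
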